1.6.6 Summary

In vitro and in vivo nonclinical xenograft experiments suggest the potential for clinical antitumor activity in INI1-negative tumors, thus providing a rational potential benefit of tazemetostat in the aforementioned pediatric tumors. Furthermore, in the Phase 1 study of tazemetostat in adults, three subjects with MRT, treated with tazemetostat 800 mg BID, have been enrolled to the ongoing adult study and have demonstrated clinical activity.

Given the available safety and initial activity data of tazemetostat in adult subjects, nonclinical safety profile, nonclinical efficacy data in xenograft models, and unmet need in pediatric patients, there is an appropriate potential benefit to risk consideration to study tazemetostat in pediatric subjects with INI1-negative tumors.

2 OBJECTIVES AND ENDPOINTS

Objectives	Endpoints
Primary: Dose Escalation	

 To determine the MTD or the RP2D of tazemetostat when administered as an oral suspension BID in pediatric subjects with relapsed/refractory rhabdoid tumors, INI1-negative tumors, or synovial sarcoma 	
 Incidence and severity of TEAEs qualifying as protocol-defined DLTs in Cycle 1 Establishment of the protocol-defined RP2D and/or MTD
Primary: Dose Expansion	

 To evaluate the antitumor activity of tazemetostat as assessed by overall response rate (ORR) in in pediatric subjects with relapsed/refractory atypical teratoid rhabdoid tumor (ATRT) (Cohort 1), non-ATRT rhabdoid tumors (Cohort 2), INI1-negative tumors (Cohort 3), and tumor types eligible for Cohorts 1 through 3 or synovial sarcoma with SS18-SSX rearrangement (Cohort 4) using disease-appropriate standardized response criteria 	
 ORR: CR + PR for each cohort
Secondary: Dose Escalation	

 To evaluate the preliminary antitumor activity of tazemetostat as assessed by ORR, using disease-appropriate standardized response criteria 	
 ORR: CR + PR
Secondary: Dose Expansion	

 To determine the PFS and overall survival (OS) at 24 and 56 weeks and overall pediatric subjects with relapsed/refractory ATRT (Cohort 1), non-ATRT rhabdoid tumors (Cohort 2), INI1-negative tumors (Cohort 3), and tumor types eligible for Cohorts 1 through 3 or synovial sarcoma with SS18-SSX rearrangement (Cohort 4) using disease-appropriate standardized response criteria 	
 PFS at 24 and 56 weeks and overall for each cohort OS at 24 and 56 weeks and overall for each cohort
Secondary: All Subjects	

 To assess the safety and tolerability of tazemetostat administered as an oral suspension BID and tablet three times daily (TID) 	
 AEs, clinical laboratory tests, and other safety measures

 To assess the pharmacokinetic (PK) parameters of tazemetostat after administrations as suspension or tablets in pediatric subjects 	
 PK parameters: maximum plasma concentration (C_{max}), time to C_{max} (T_{max}), area under the concentration-time curve from time 0 to last measurable concentration [$AUC_{(0-t)}$], area under the concentration-time curve from time 0 to 12 hours post-dose [$AUC_{(0-12)}$], elimination half-life ($t_{1/2}$), oral clearance (CL/F), oral volume of distribution (Vd/F), first-order absorption rate constant (Ka); if data permit

 To evaluate the duration of response in subjects achieving a CR or PR according to disease-appropriate standardized response criteria 	
 Response duration

Objectives	Endpoints
Exploratory: All Subjects	
CCI	

3 STUDY DESIGN

3.1 Overall Experimental Plan

This is a Phase 1, multicenter, open-label, dose escalation and expansion study of tazemetostat in pediatric subjects with select relapsed or refractory INI1- or SMARCA4-negative tumors. Subjects will be screened for eligibility within 14 days of the planned first dose of tazemetostat. A treatment cycle will be 28 days. Treatment with tazemetostat will continue until disease progression, unacceptable toxicity, or withdrawal of consent. Subjects will receive tazemetostat for a cumulative maximum of 2 years.

3.2 Dose Escalation Phase

The starting dose for the dose escalation phase will be 240 mg/m²/dose administered orally BID for a total of 480 mg/m²/day. Dose escalation will proceed in increments of 25%-33% and dose de-escalation will proceed in decrements of 50%.

Table 4. Dose Escalation

Dose Level	Dose of Tazemetostat
Level 0	120 mg/m ² BID = 240 mg/m ² /day
Level 1 (starting dose)	240 mg/m ² BID (starting dose) = 480 mg/m ² /day
Level 2	300 mg/m ² BID = 600 mg/m ² /day
Level 3	400 mg/m ² BID = 800 mg/m ² /day
Level 4	520 mg/m ² BID = 1040 mg/m ² /day
Level 5	700 mg/m ² BID = 1400 mg/m ² /day
Level 6	900 mg/m ² BID = 1800 mg/m ² /day
Level 7	1200 mg/m ² BID = 2400 mg/m ² /day
Level 8	1600 mg/m ² BID = 3200 mg/m ² /day

Abbreviation: BID=twice daily.

A “Rolling 6” dose-escalation design (Table 5) (Skolnik, 2008) will be employed whereby up to six subjects may be concurrently enrolled onto the study. Accrual to the study will only be suspended when awaiting data from six subjects. All safety data during dose escalation will be assessed in real time with appropriate adjustments to enrollment if toxicity is seen. For dose-escalation decisions, a minimum of 22 days of toxicity data (80% of one cycle) must be available for each subject.

Decisions as to whether to enroll a new subject onto the current, next highest, or next lowest dose level will be made based on available data at the time of new subject enrollment and will be made by the CSRC (see Section 11). The dose level assigned will be based on the number of subjects currently enrolled in the cohort, the number of DLTs observed, and the number of subjects at risk for developing a DLT (i.e., subjects enrolled, but who were not yet evaluable for toxicity).

Table 5. Rolling 6 Dose Escalation/De-Escalation Parameters

Subjects Enrolled	# Subjects with DLT	# Subjects without DLT	# Subjects with Toxicity Data Pending	Decision When Next Subject Enrolled
2	0, 1	Any	Any	Stay
2	2	0	0	De-escalate
3	0	0, 1, 2	3, 2, 1	Stay
3	0	3	0	Escalate
3	1	0, 1, 2	2, 1, 0	Stay
3	≥2	Any	Any	De-escalate
4	0	0, 1, 2, 3	4, 3, 2, 1	Stay
4	0	4	0	Escalate
4	1	0, 1, 2, 3	3, 2, 1, 0	Stay
4	≥2	Any	Any	De-escalate
5	0	0, 1, 2, 3, 4	5, 4, 3, 2, 1	Stay
5	0	5	0	Escalate
5	1	0, 1, 2, 3, 4	4, 3, 2, 1, 0	Stay
5	≥2	Any	Any	De-escalate
6	0	0, 1, 2, 3, 4	6, 5, 4, 3, 2	Suspend
6	0	5, 6	1, 0	Escalate
6	1	0, 1, 2, 3, 4	5, 4, 3, 2, 1	Suspend
6	1	5	0	Escalate
6	≥2	Any	Any	De-escalate

Abbreviation: DLT=dose-limiting toxicity

The MTD will be determined based on the incidence of DLTs in Cycle 1, although toxicities occurring in subsequent cycles will also be reviewed. If serious toxicities are observed at the MTD in later cycles, a reduction of the MTD may be considered.

3.3 Dose Expansion Phase

For new patient dosing, refer to Section 5.3. Subjects will be enrolled into the following cohorts:

- Cohort 1 – Subjects with ATRT (closed to enrollment)
- Cohort 2 – Subjects with MRT/RTK/select tumors with rhabdoid features
- Cohort 3 – Subjects with INI1-negative tumors
- Cohort 4 – Subjects with one of the tumor types defined in Cohorts 1 through 3 or synovial sarcoma with SS18-SSX rearrangement (closed to enrollment)

Note, as initially designed, the dose expansion portion of the study was to enroll only subjects with rhabdoid tumors. This group has been divided into two separate cohorts (Cohort 1 and

Cohort 2) as initial subject screening and enrollment trends into the dose-escalation portion of the study indicate that enrollment would be heavily weighted toward ATRT tumor types, therefore, losing the potential to evaluate subjects with non-CNS rhabdoid tumors such as MRT and RTK. Cohort 1 is now closed to enrollment. In addition, as subjects with INI1-negative tumors are being enrolled into the dose-escalation portion of the study, Cohort 3 has been added to the expansion portion of the study in order to evaluate for antitumor response that may be missed in the dose-escalation portion of the study. For these reasons, as well as antitumor activity seen in the current Phase 1 and ongoing Phase 2 studies in adults with INI1-negative tumors and synovial sarcoma, Cohorts 1, 2, and 3 were added as part of Amendment 3. In addition, Cohort 4 was added as part of Amendment 5 to evaluate the administration of tazemetostat in tablet formulation to pediatric subjects who can swallow tablets, which may be more palatable. Cohort 4 is now closed to enrollment.

3.4 Rules for Suspension of Enrollment and Dosing

3.4.1 Rules for Suspension in Any Phase

The Investigators, Institutional Review Board (IRB)/Ethics Committee (EC), regulatory agencies, and CSRC will be urgently informed and the Quarterly Safety Review (QSR) committee promptly convened to review the data and to make recommendations for potential changes in study conduct, including suspension of dose escalation or expansion. The rule will be set in motion if one or more subjects develop any of the following AEs deemed to be definitely related to study treatment by the Investigator and/or Medical Monitor, based upon close temporal relationship or other factors:

- Death
- Anaphylaxis (angioedema, hypotension, shock, bronchospasm, hypoxia, or respiratory distress)
- CCI /T-ALL

If a new case of CCI /T-ALL occurs, the patient will be discontinued from treatment, and enrollment of new patients will be suspended. The risk/benefit of the drug will be assessed via an ad hoc QSR and a decision will be made (continue the study or not). The study will not be restarted until QSR has made a decision and has agreed upon a course of action. Following the decision, and as per QSR charter, communication to Health Authorities, IRBs/ECs and Investigators will occur. However, patients on study who continue to derive clinical benefit at this time will be maintained on therapy. For more details on AESIs, refer to Section 10.4.

3.4.2 Rules for Suspension of Dose Expansion

The CSRC will convene to review the aggregate safety experience and to assess termination of dose expansion if any of the DLT conditions (see Section 6.3) are met in $\geq 33\%$ subjects in a cohort. Special attention will be paid to AEs associated with bromide toxicity, as well as bromide values in the range associated with severe bromide toxicity, and AESIs (see Section 10.4). The CSRC may also recommend suspension of tazemetostat dose expansion based upon other conditions as deemed medically appropriate.

3.5 Estimated Study Duration

3.5.1 Study Duration for Participants

The study duration is approximately 24 months for each subject. The duration of screening for each subject will be approximately 14 days. The subject accrual period is planned for approximately 15 months. The duration of treatment will vary for each subject. Subjects may receive tazemetostat for a cumulative maximum of 2 years. Subjects will be followed for safety for approximately 30 days after the last dose of tazemetostat. For subjects that discontinue dosing, participation will continue for survival follow-up and response for 2 years from first dose of tazemetostat.

3.5.2 End of Study

Primary completion: This includes time until the last subject is assessed or receives an intervention for the purposes of final collection of data for the primary analysis of the study. The primary completion is expected to occur approximately 6 months after the date the last subject is enrolled to treatment and evaluated for response.

End of study: This includes time when the last subject is assessed or receives an intervention for evaluation in the study. The end of study will occur when the last subject discontinues the study treatment and has had the opportunity to complete the safety follow-up visit or the long-term survival follow-up period, whichever is later. The study may end prior to this if 80% of enrolled subjects are deceased prior to the collection of the last survival follow-up.

4 SUBJECT POPULATION

4.1 Number of Subjects

A total of approximately 120 subjects will be enrolled in this study. Up to 48 subjects are estimated to be enrolled during dose escalation (subjects who discontinue in absence of a DLT prior to the completing of the DLT evaluation period may be replaced). Up to 72 subjects are estimated to be enrolled during Dose Expansion. See Section 14.2.1 for sample size assumptions.

Immunotherapy (e.g., tumor vaccine)	At least 6 weeks since last dose of immunotherapy agent(s) prior to the first dose of tazemetostat
Radiotherapy (RT)	At least 14 days from last local site RT prior to first dose of tazemetostat At least 21 days from stereotactic radiosurgery prior to first dose of tazemetostat At least 12 weeks from craniospinal, $\geq 50\%$ radiation of pelvis, or total body irradiation prior to first dose of tazemetostat
Hematopoietic growth factor	At least 14 days from last dose of hematopoietic growth factor prior to the first dose of tazemetostat
Hematopoietic cell transplantation (allogeneic or autologous)	At least 60 days from infusion of hematopoietic cells prior to the first dose of tazemetostat

10. Has adequate hematologic (bone marrow and coagulation factors), renal and hepatic function as defined by criteria below:

System	Laboratory Value	
Hematologic (BM Function)		
Hemoglobin ^a	≥ 8 g/dL	
Platelets ^b	$\geq 100,000/\text{mm}^3$ ($\geq 100 \times 10^9/\text{L}$)	
ANC ^c	$\geq 1000/\text{mm}^3$ ($\geq 1.0 \times 10^9/\text{L}$)	
Hematologic (Coagulation Factors)		
INR/PT ^d	≤ 1.5 ULN	
PTT	≤ 1.5 ULN	
Renal Function		
Calculated Creatinine Clearance ^e	≥ 50 mL/min/1.73 m ²	
OR		
Serum creatinine based on age/gender		
AGE	Male	Female
6 months to 1 year	0.6 mg/dL (53 $\mu\text{mol}/\text{L}$)	0.5 mg/dL (44 $\mu\text{mol}/\text{L}$)
1 to <2 years	0.6 mg/dL (53 $\mu\text{mol}/\text{L}$)	0.6 mg/dL (53 $\mu\text{mol}/\text{L}$)
2 to <6 years	0.8 mg/dL (71 $\mu\text{mol}/\text{L}$)	0.8 mg/dL (71 $\mu\text{mol}/\text{L}$)
6 to <10 years	1 mg/dL (88 $\mu\text{mol}/\text{L}$)	1 mg/dL (88 $\mu\text{mol}/\text{L}$)
10 to <13 years	1.2 mg/dL (106 $\mu\text{mol}/\text{L}$)	1.2 mg/dL (106 $\mu\text{mol}/\text{L}$)
13 to <16 years	1.5 mg/dL (133 $\mu\text{mol}/\text{L}$)	1.4 mg/dL (124 $\mu\text{mol}/\text{L}$)

≥16 years	1.7 mg/dL (150 μmol/L)	1.4 mg/dL (124 μmol/L)
Hepatic Function		
Total bilirubin ^f	<1.5 × ULN for age	
ALT or AST ^g	<3 × ULN	

Abbreviations: ALT, alanine aminotransferase; ANC, absolute neutrophil count; AST, aspartate aminotransferase; BM, bone marrow; INR, international normalized ratio; LLN, lower limit of normal; PT, prothrombin time; PTT, partial thromboplastin time; ULN, upper limit of normal

- a. May receive transfusion
- b. Should be evaluated after at least 7 days since last platelet transfusion
- c. Without growth factor support (filgrastim or pegfilgrastim) for at least 14 days
- d. INR is the preferred value to be measured but if only PT can be performed in the testing laboratory that is acceptable
- e. Creatinine clearance by 24-hour urine or radioisotope glomerular filtration rate
- f. Eligibility can be determined by either total or conjugated bilirubin
- g. If attributed to tumor involvement, AST and ALT <5xULN

NOTE: Laboratory results obtained during Screening should be used to determine eligibility criteria. In situations where laboratory results are outside the permitted range, the Investigator may retest the subject and the subsequent within range Screening result may be used to determine the subject's eligibility.

11. For subjects with CNS involvement: Subjects must have:

- Deficits that are stable for a minimum of 14 days prior to first dose of study drug, or
- Seizures that are stable, not increasing in frequency or severity and controlled on current anti-seizure medication(s) for a minimum of 7 days prior to first dose of study drug, or
- Treated brain metastases without evidence of progression (new or enlarging brain metastases by imaging 4 weeks prior to the first dose of study drug), and are on stable or tapering doses of steroids for at least 7 days prior to first dose of study drug.

NOTE: Subjects with leptomeningeal disease or brain tumors with positive cerebral spinal fluid cytology are eligible for this study. Subjects may receive glucocorticoids (at stable or tapering dose) to control CNS symptoms prior to enrollment; however, subjects should receive a stable or tapering dose for at least 7 days prior to first dose of study drug.

12. Has a left ventricular (LV) fractional shortening of >27% or an LV ejection fraction of ≥50% by echocardiogram (ECHO) or multigated acquisition scan (MUGA) and New York Heart Association Class ≤2.
13. Has a QT interval corrected by Fridericia's formula (QTcF) ≤450 msec
14. Is able to swallow and retain orally administered medication and does not have any uncontrolled gastrointestinal (GI) condition such as nausea, vomiting or diarrhea, or any

clinically significant GI abnormalities that may alter absorption such as malabsorption syndromes, hereditary fructose intolerance, glucose-galactose malabsorption, sucrose-isomaltase insufficiency, or major resection of the stomach and/or bowels.

NOTE: Nasogastric and gastrostomy tube administration of the oral suspension formulation of study drug is permitted.

15. Has sufficient tumor tissue (slides or blocks) available for central confirmatory testing of immunohistochemistry (IHC) and/or cytogenetics/FISH and/or DNA mutation analysis (required for study entry but enrollment based on local results).
16. Is willing and able to comply with all aspects of the protocol as judged by Investigator.
17. **For female subjects of childbearing potential:** Subject must:
 - Have a negative beta-human chorionic gonadotropin (β -hCG) pregnancy test at time of Screening and within 72 hours prior to planned first dose of tazemetostat (urine or serum test is acceptable however, positive urine tests must be confirmed with serum testing), and
 - Agree to use effective non-hormonal contraception, as defined in Section 8.5.11 from start of Screening until 6 months following the last dose of study treatment and have a male partner who uses a condom, or
 - Practice true abstinence (when this is in line with the preferred and usual lifestyle of the subject, see Section 8.5.11), or
 - Have a male partner who is vasectomized with confirmed azoospermia.
18. **For male subjects with a female partner of childbearing potential:** Subject must:
 - Be vasectomized or
 - Agree to use condoms as defined in Section 8.5.11 from the first dose of tazemetostat until 3 months following the last dose of tazemetostat, or
 - Have a female partner who is NOT of childbearing potential
19. **For subjects enrolling at sites in France only:** Is either affiliated with or a beneficiary of a social security category

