13 to <16 years	1.5 mg/dL (133 μmol/L)	1.4 mg/dL (124 μmol/L)
≥16 years	1.7 mg/dL (150 μmol/L)	1.4 mg/dL (124 μmol/L)
Hepatic Function		
Total bilirubin ^f	<1.5 × ULN for age	
ALT or AST ^g	<3 × ULN	

Abbreviations: ALT, alanine aminotransferase; ANC, absolute neutrophil count; AST, aspartate aminotransferase; BM, bone marrow; INR, international normalized ratio; LLN, lower limit of normal; PT, prothrombin time; PTT, partial thromboplastin time; ULN, upper limit of normal

- a. May receive transfusion
- b. Should be evaluated after at least 7 days since last platelet transfusion
- c. Without growth factor support (filgrastim or pegfilgrastim) for at least 14 days
- d. INR is the preferred value to be measured but if only PT can be performed in the testing laboratory that is acceptable
- e. Creatinine clearance by 24-hour urine or radioisotope glomerular filtration rate
- f. Eligibility can be determined by either total or conjugated bilirubin
- g. If attributed to tumor involvement, AST and ALT $<5 \times$ ULN

NOTE: Laboratory results obtained during Screening should be used to determine eligibility criteria. In situations where laboratory results are outside the permitted range, the Investigator may retest the subject and the subsequent within range Screening result may be used to determine the subject's eligibility.

11. **For subjects with CNS involvement:** Subjects must have:

- Deficits that are stable for a minimum of 14 days prior to first dose of study drug, or
- Seizures that are stable, not increasing in frequency or severity and controlled on current anti-seizure medication(s) for a minimum of 7 days prior to first dose of study drug, or
- Treated brain metastases without evidence of progression (new or enlarging brain metastases by imaging 4 weeks prior to the first dose of study drug) and are on stable or tapering doses of steroids for at least 7 days prior to first dose of study drug.

NOTE: Subjects with leptomeningeal disease or brain tumors with positive cerebral spinal fluid cytology are eligible for this study. Subjects may receive glucocorticoids (at stable or tapering dose) to control CNS symptoms prior to enrollment; however, subjects should receive a stable or tapering dose for at least 7 days prior to first dose of study drug.

12. Has a left ventricular (LV) fractional shortening of $>27\%$ or an LV ejection fraction of $\geq 50\%$ by echocardiogram or multigated acquisition scan and New York Heart Association Class ≤ 2

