1.6.5 Anticipated Safety Profile

This section summarizes the anticipated safety profile for tazemetostat based on the clinical experience in 90 pediatric subjects treated as of 24 May 2019 in this ongoing study (EZH-102), on nonclinical toxicology studies, and where noted, on 725 adult subjects treated with tazemetostat.

The following treatment-emergent AEs, regardless of causality, have been observed in $\geq 10\%$ of pediatric subjects in study EZH-102: vomiting, nausea, fatigue, diarrhea, and anemia.

The following nonserious adverse reactions to tazemetostat treatment have been observed in $\geq 2\%$ of pediatric subjects in study EZH-102: vomiting, nausea, fatigue, diarrhea, anemia, decreased appetite, constipation, thrombocytopenia, and neutropenia.

Tazemetostat treatment-related SAEs have been reported in 9 (10%) pediatric subjects in study EZH-102. The only serious adverse reaction reported in ≥ 1 pediatric subject has been decreased appetite (2 subjects).

The most common TEAEs that have led to interruption of tazemetostat dosing in pediatric subjects were: platelet count decreased (7%); hydrocephalus (6%); and thrombocytopenia, neutropenia, diarrhea, intestinal obstruction, dyspnea, hypoxia, and pyrexia (each 2%). The most common TEAEs leading to dose reduction in pediatric subjects have been platelet count decreased and thrombocytopenia, reported in 3 (3%) subjects and 2 (2%), respectively.

In addition, as described in Section 10.4, AESIs identified for the tazemetostat development program include: CCI /T-ALL, MDS, AML, and other myeloid malignancies like MPN. Epizyme considers the risk for CCI /T-ALL in tazemetostat clinical trials to be largely concentrated in pediatric patients. Myeloid malignancies have been reported in 5 of the 725 subjects in the adult population treated with tazemetostat. The risk of myeloid neoplasias as a result of EZH2 inhibition is considered uncertain based on available literature and Epizyme clinical data. Measures are in place to exclude potential subjects who may be predisposed to developing a myeloid neoplasia from participation in clinical studies and for early identification and monitoring of subjects who may be developing a myeloid neoplasia.

Further details of clinical study designs, tazemetostat exposure, and treatment-emergent AEs regardless of causality are outlined in the current IB.

Additionally, there are unknown risks of abnormal pregnancy outcomes and drug-drug interactions.

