8.5.10 Clinical Laboratory Assessments

All clinical laboratory assays will be performed at local laboratories according to the laboratory's normal procedures. Chloride levels will be analyzed at both local and central laboratories. Bromide will be collected and sent only to a central laboratory for analysis. Please see Laboratory Manual for details. Reference ranges will be supplied by the laboratory and used to assess the laboratory data for clinical significance and out of range pathological changes. Abnormal laboratory values which are unexpected or not explained by the subject's clinical condition should be repeated until confirmed, explained, or resolved. Laboratory value changes starting from the initial tazemetostat exposure will be recorded in the eCRF as an AE if clinically significant.

Hematology: Hemoglobin, hematocrit, WBC, differential blood count with ANC, and platelet count assessments are performed at Screening and at regular intervals during each treatment cycle. Also, a peripheral blood smear will be collected along with normal hematology testing at screening and on day 1 of each cycle and assessed for abnormal morphology and potential bone marrow aspirate/biopsy (see below).

Coagulation Profile: Partial thromboplastin (PT), partial thromboplastin time (PTT), and international normalized ratio (INR) are performed at Screening, as clinically indicated (for example, when an anticoagulant is started or when total bilirubin increases to 1.5 X ULN), and at Post-treatment/Early Termination.

Serum Chemistry: Serum chemistries will be performed at Screening and at regular intervals during each treatment cycle.

- Chemistries (liver function) include: alkaline phosphatase, ALT, AST, and either conjugated (direct) bilirubin (where possible), or total bilirubin
- Chemistries (renal function) include: blood urea nitrogen, creatinine, electrolytes including sodium, potassium, chloride, and bicarbonate
- Chemistries (metabolism) include: albumin, calcium, magnesium, glucose, phosphorus, total protein, and triglycerides

Bromide Levels: Bromide levels will be measured pre-dose on Day 1 of Cycle 1; on Day 1 of every cycle thereafter; and at Post-Treatment/Early Termination visit.

Urinalysis: Urinalysis testing to include at minimum: glucose, blood, protein, and pH will be performed at Screening, on Cycle 1, Day 1, and on Day 1 every cycle thereafter and at Post-Treatment/Early Termination visit.

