10. PROTOCOL DEVIATIONS

Protocol deviations will be summarized by major and minor category and by study part for the ITT population. All protocol deviations will be listed for the ITT population. Predefined categories of major protocol deviations include:

- Violation of inclusion/exclusion criteria
- Prohibited medications
- Study drug compliance

Additional categories may be added during the course of the study but will be determined prior to database lock.

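### Inclusion criterion 10 contradicts itself on liver enzymes: the base row, read literally, caps only one of ALT and AST, while its tumor-involvement relaxation caps both (minor)

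*Protocol*

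**What the plan says.** Protocol Section 4.2, inclusion criterion 10, requires adequate "renal and hepatic function as defined by criteria below", so the table beneath it is the definition of adequate liver function. The enzyme row of that table names ALT or AST with a limit of <3 × ULN and carries footnote g: "If attributed to tumor involvement, AST and ALT <5xULN". The Synopsis repeats both the row and the footnote.

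Elsewhere the same table says openly when one of two tests is enough:

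- Renal function has a separate OR line between creatinine clearance and serum creatinine.
- Footnote d accepts PT where a laboratory cannot report INR.
- Footnote f says of bilirubin: "Eligibility can be determined by either total or conjugated bilirubin".

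No such statement is made for ALT and AST. Both are on the required panel in Protocol Section 8.5.10: "Chemistries (liver function) include: alkaline phosphatase, ALT, AST, and either conjugated (direct) bilirubin (where possible), or total bilirubin".

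SAP Section 10 names "Violation of inclusion/exclusion criteria" as a predefined category of major protocol deviation.

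**The concern.** The conjunction changes from *or* in the base row to *and* in the footnote that relaxes it. With *or* taken at face value, one acceptable enzyme is enough and the other has no ceiling. The tumor-involvement allowance, which should only widen entry, then becomes the stricter rule for some children.

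Two things follow. A child with one markedly raised enzyme could be enrolled by a site that applies the row as written. And with 20 to 30 sites planned (Synopsis), two sites could reach opposite decisions on the same laboratory results. That child would be an eligibility deviation under one reading and no deviation under the other.

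Other criteria narrow the gap without closing it:

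- Inclusion 8 covers only toxicity from prior treatment, and lets it stand above Grade 1 if it is stable and clinically unimportant.
- The bilirubin and INR/PT limits, the hepatitis B and C exclusion and the intercurrent-illness exclusion set no ALT or AST value.

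**Working it through.** The plan gives no figure to reproduce here. The check is whether the rules fit together.

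**Inputs.** Base limit 3 × ULN joined by *or* (Section 4.2 and Synopsis, hepatic row). Relaxed limit 5 × ULN joined by *and* (footnote g in both places). The enzyme values below are assumed for illustration, in multiples of ULN.

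**Rules as formulas.**

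- Literal base row: min(ALT, AST) < 3
- Base row read as each enzyme: max(ALT, AST) < 3
- Footnote g: max(ALT, AST) < 5

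**Cases.**

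| Case | ALT | AST | Literal row | Each < 3 | Footnote g |
|---|---|---|---|---|---|
| 1 | 2 | 2 | met | met | met |
| 2 | 4 | 2 | met (min = 2) | not met (max = 4) | met |
| 3 | 10 | 2 | met (min = 2) | not met (max = 10) | not met (max = 10) |
| 4 | 4 | 4 | not met (min = 4) | not met (max = 4) | met |

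**Reading the table.** Case 4 is what a relaxation is for: it fails the base rule and passes footnote g. Case 3 is the fault: it passes the base rule and fails footnote g. More generally, any child with one enzyme below 3 and the other at 5 or more meets the literal row and fails the footnote. If footnote g replaces the row whenever the rise is attributed to tumor, such a child is refused when the tumor explains the enzyme and accepted when it does not.

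Case 2 shows where sites could differ over a smaller rise. Without tumor involvement, the literal row admits the child and the each-enzyme reading does not.

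**After correction.** If both enzymes are below 3, both are below 5. The base rule then lies wholly inside footnote g, and the footnote can only widen entry.

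**The case against.** The strongest reply is that the table already settles the reading. Relaxing both enzymes to 5 × ULN makes sense only against a base limit on both. Where the table means a true alternative it says so, through the renal OR line and footnotes d and f. The row label can also be read as meaning whichever enzyme is in question. This is a good account of the intent, and many sites would probably read the row that way. A reader might infer the opposite, that the plan deliberately leaves one enzyme uncapped. The documents do not support that, for the reasons just given. What remains is that the row does not state the each-enzyme rule, and the renal OR in the same table gives a site a precedent for the literal sense.

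Second, Protocol Section 15.5 sends eligibility questions to the Medical Monitor. That is a real safeguard, but it works only when a site notices the doubt. The Day 1 chemistry review before dosing (Section 8.5.10) does not help, because it reconfirms eligibility against the same row.

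Third, a reader might infer from the major-deviation category that trial results are at risk. They are not. The ITT population is everyone who received at least one dose (Protocol Section 14.3.1, SAP Section 5), and the SAP defines no per-protocol set. SAP Section 1 also requires deviations to be identified before analysis, which lets the sponsor apply one reading to all sites. The effect stops at the deviation summary and listing.

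**Conclusion.** The inconsistency is real and the row is wrong as written, but the point is minor. It rests on the literal wording of the operative eligibility table, which is the same in the Synopsis and Section 4.2, and on the absence of any other ALT or AST limit. Each enzyme below 3 × ULN is the likely intent.

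The consequence is limited to possible entry of a child with one markedly raised enzyme and inconsistent listing of eligibility deviations. The response-rate analysis, the requirement of 3 responders in 20, the sample size and the error rates are untouched.

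The documents give no count of children with discordant enzymes, and it may be zero. A reader might infer how many children a correction could still reach by subtracting those already treated from the planned total. That would not be a reliable bound: both the study total and the cohort sizes are approximate, and enrollment by cohort is not reported apart from the 4 children given tablets in Cohort 4.

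**What to change.** In both the Synopsis and Section 4.2, replace the enzyme row and footnote g with: **ALT and AST each <3 × ULN (each <5 × ULN if attributed to tumor involvement)**.

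This is one line in two places and can go into the next amendment. If enrollment has ended by then, a written clarification would serve. The same reading should be used when deviations are classified for children already enrolled. No new test is needed, since both enzymes are already required. The downside is possibly a few more screen failures at sites that have been reading the row literally.
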